12 ASSESSMENT OF SAFETY

12.1 Definitions

12.1.1 Adverse Event (AE)

Any untoward medical occurrence in a patient administered a medicinal product and which does not necessarily have a causal relationship with this treatment.

An adverse event (AE) can therefore be any unfavourable and unintended sign (including an abnormal laboratory finding), symptom, or disease temporarily associated with the use of a medicinal (investigational) product, whether or not related to the medicinal (investigational) product. Not all adverse events are adverse reactions but all adverse reactions are adverse events.

12.1.2 Adverse Drug Reaction (ADR) to an Investigational Medicinal Product (IMP)

An Adverse Drug Reaction is any untoward and unintended response in a participant to an IMP which is related to any dose administered to that participant. Any adverse event judged by either the reporting Investigator or Sponsor as having causal relationship to an IMP qualifies as an ADR.

All adverse reactions are adverse events.

12.1.3 Serious Adverse Event (SAE)

Any untoward medical occurrence that at any dose:

- Results in death
- Is life threatening,
- Requires inpatient hospitalisation or prolongation of existing hospitalization,
- Results in persistent or significant disability/incapacity, or
- Is a congenital anomaly/birth defect`

'Important medical events' may also be considered serious if they jeopardise the patient or require an intervention to prevent one of the above consequences.

The term 'life-threatening' in the definition of serious refers to an event in which the subject was at risk of death at the time of event; it does not refer to an event which hypothetically might have caused death if it were more severe.

Hospitalisations for pre-planned procedures do not require reporting as an SAE, unless the condition worsens.

12.1.4 Serious Adverse Reaction

An Adverse Reaction which also meets the definition of a Serious Adverse Event.

12.1.5 Suspected Unexpected Serious Adverse Reaction (SUSAR)

A SUSAR is a serious ADR where the reaction to an IMP that is not consistent with the applicable product information highlighted in the Investigators brochure for an unapproved investigational product or package insert/summary of product characteristics for an approved product. For this trial, the Summary of Product Characteristics (SPC) will be the reference document.

12.2 Reporting Requirements and Procedure

The collection and reporting of Adverse Events (AEs) will be in accordance with the Medicines for Human Use Clinical Trials Regulations 2004 and it's subsequent amendments.

All medical occurrences which meet the definition of an AE that occur during the trial will be recorded. All adverse events must be assessed for seriousness and causality.

The following methods will be used to collect adverse events in this trial:

12.2.1 Adverse Events

1) AEs which are pre-specified outcomes of the trial.

The following AEs are pre-specified outcomes for the trial: nausea, vomiting, hearing problems, dizziness and rash.

These adverse events will be collected on the eCRF following targeted questioning by a member of the research team during the follow-up visit at two weeks.

Any of the above events which meet the definition of serious will also require reporting on a serious adverse event form (see section 12.2.2)

Creatinine levels will be collected at baseline and at the 2 week follow-up visit. If changes in these levels are of clinical concern, they should be reported as AEs.

2) Other Adverse Events

Participants will be asked at their two week follow-up visit whether they have experienced any other adverse events. All adverse events experienced by the patient (apart from those specified above which are pre-specified outcomes for the trial) must be recorded on the Adverse Event eCRF at the two week follow-up visit.

Injection site pain should not be recorded as an Adverse Event. This is captured elsewhere on the eCRF.

Any events which meet the definition of serious will also require reporting on a serious adverse event form (see section 12.2.2)

12.2.2 Serious Adverse Events

Participants will be asked to contact the research team at site immediately in the event of any serious adverse event and will also be asked at their follow-up visit if they have experienced any adverse events.

The Investigator must report any AEs that meet the definition of a serious adverse event (SAE). Serious Adverse Events must be reported to the Nottingham Clinical Trials Unit within 24 hours of becoming aware of the SAE.

The Investigator must assess the seriousness and causality of all AEs experienced by the patient.

Further instructions on reporting SAEs are contained in the Trial Manual.

12.2.3 Assessment of expectedness

Upon receipt by the NCTU, the Chief Investigator will assess all serious adverse events for expectedness in relation to the Reference Safety Information.

12.3 Follow-up of serious adverse events

Serious adverse events will be monitored until resolution or stabilisation.

12.4 Reporting Period

Details of all AEs will be documented and reported from the date of consent until completion of the follow-up visit at two-weeks. If a patient fails to return to clinic for their follow-up visit despite reminders, adverse event data will be assumed to be lost to follow up and missing at random.

12.5 Pregnancy

Pregnant patients are excluded from entering the trial. All women will have a pregnancy test prior to administration of the study drug. Given that the study drug is a single dose and the half-lives of gentamicin and ceftriaxone are about 2-3 hours and 8 hours, respectively there will be negligible risk after 24 hours, thus no specific pregnancy monitoring is deemed necessary in this study.

Participants are advised to avoid sexual intercourse for 7 days and until their sexual partner has also been evaluated and tested negative or received treatment.

12.6 Reporting to Sponsor, MHRA and Ethics Committee

The Nottingham Clinical Trials Unit will report all serious adverse events to the Sponsor within 24 hours of the event being reported.

The Nottingham Clinical Trials Unit will produce an annual report which includes a listing of all serious adverse reactions (SARs) and a summary report of the patients' safety and submit this within the required timeframes. A copy of the annual safety report will also be sent by Nottingham Clinical Trials Unit to the Sponsor.

Any SUSARs that occur during the course of the trial will be reported by the NCTU within the required timeframes to the MHRA and REC. The Sponsor will be notified by NCTU within 24

hours of becoming aware of a SUSAR and sent a copy of the report submitted to the MHRA/REC.

The Nottingham Clinical Trials Unit will also notify investigators at all trial sites of any SUSARs that occur after the Sponsor has been informed.

13 TRIAL CLOSURE

Planned trial closure will be when all randomised participants have had their follow up visit (Visit 2) and all data associated with that visit has been recorded on the database.

The Chief Investigator may stop the trial or terminate one or more centres if new information becomes available causing major safety concerns or if there are issues with trial conduct.

If recruitment and/or retention fail to reach the rates predicted, despite implementation of improvement strategies, the trial may be terminated.

14 STATISTICAL CONSIDERATIONS

The analysis and reporting of the trial will be in accordance with CONSORT guidelines. A full statistical analysis plan will be developed prior to completion of data collection.

14.1 Sample size

Based on an efficacy rate of 96% for the ceftriaxone regimen which is consistent with previous trials, a total sample size of 646 for analysis (323 in each group) will achieve 90% power to detect non-inferiority with lower confidence limit for the absolute risk difference of 5%. The significance level is 0.025. To allow for a loss to follow-up rate of up to 10%, the study will recruit a total of 720 participants. A 5% lower confidence interval was acceptable to 17 of 24 sexual health patients whose opinion was sought, and provides a realistic recruitment target.

14.2 Statistical Analysis

Continuous variables will be summarised in terms of the mean, standard deviation, median, lower and upper quartiles, minimum, maximum and number of observations. Categorical variables will be summarised in terms of frequency counts and percentages. Descriptive statistics of demographic and clinical measures will be used to compare balance between the randomised arms at baseline.

The primary approach to between-group comparative analyses will be by intention-to-treat without imputation of missing outcome data. Sensitivity analyses will be conducted to investigate the impact of missing primary outcome data, using simple and multiple imputation. Due to both interventions being single dose administered immediately following randomisation, non-adherence with treatment allocation is expected to be negligible. Therefore additional sensitivity analyses that aim to estimate treatment effect among those who have adhered with allocation are not expected to be required.

The evaluation of the primary clinical outcome variable will be performed using a general linear model for binary outcome adjusted by clinic site. The primary efficacy parameter

comparing gentamicin with ceftriaxone will be the risk difference in the proportion of participants clear of infection at two weeks follow up along with the 95% confidence interval. Gentamicin will be regarded as non-inferior if the lower 95% confidence limit for the risk difference in confirmed clearance is -5 percentage points or greater.

Secondary outcomes will be similarly analysed using appropriate regression models dependent on data type (binary, continuous etc), adjusted for clinic site and baseline value of the outcome variable if collected.

We are interested in whether treatment efficacy differs by site of infection. Participants may have infection at multiple sites, and up to seven different combinations of 1/2/3 sites are possible. For each of the three infection sites, we will separately estimate clearance by treatment arm along with 95% confidence intervals, rather than formally fit an interaction term for different combinations of infection site in the regression model. Any suggestion of a differential effect according to infected site would require confirmation in future research.

Safety and tolerability analysis will be of descriptive nature. Frequency counts and percentages of the per-specified main categories of side effects and AEs will be presented by treatment arm.

No formal interim analyses are planned for this trial.

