6.3 Subject Withdrawal

Participants can be discontinued at any part of the study at any point in the study. They may withdraw themselves or may be withdrawn by a physician.

Withdrawal from treatment

Given that there is only one dose of medication given and that this is administered in close proximity to randomisation, it is unlikely that a participant would withdraw their consent to treatment. If the participant did withdraw they would be treated according to their local clinical protocol. In line with the intention to treat principle, they would be asked to come back to clinic 2 weeks after to complete the study assessments.

Withdrawal from Follow-up

Participants will be encouraged to attend for their follow-up visit, 2 weeks after treatment. However, they are free to withdraw from the study and therefore the follow-up assessment. They will be asked their reason(s) for withdrawal but are not obliged to provide these. Unless a participant specifically asks, untested samples will be tested and included in the analyses.

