10.2 Laboratory assessments

Table 2 provides a summary of the laboratory samples to be taken.

Table 2 Laboratory samples

Table 2 Laboratory samples	Symptomatic	Asymptomatic	All	
	Visit 1	Visit 1	Visit 2	
PRE-TRIAL				
Routine swabs for microscopy	✓			
Routine swabs for local NAAT	✓	✓		
Routine swabs for local culture	✓	✓		
AFTER CO	ONSENT			
Swabs				
Additional swabs to make up full sampling	✓			
profile for local NAAT				
Additional swabs to make up full sampling	✓			
profile for local culture				
Full sampling profile for local NAAT		✓		
Full sampling profile for local culture		✓		
Full sampling profile for AC NAAT at STBRU	✓	✓		
(for centres who do not perform AC NAAT)				
Swabs from infected sites for microscopy			✓	
Swabs from infected sites for NAAT			✓	
Swabs from infected sites for local culture			✓	
Swabs from infected sites for AC NAAT at			\checkmark	
STBRU (for centres who do not perform AC				
NAAT)				
Blood				
2-3ml for creatinine levels	√	√	✓	
28ml for storage for immune study	✓	✓	✓	
10ml for pharmacokinetic analysis (optional)	✓	✓		

Routine samples should be analysed in local laboratories according to local practice.

The clinical management of the participant will be based on the results of local laboratory testing.

Additional samples to make up the full sampling profile for local NAAT and local culture will be analysed in local laboratories according to local practice.

For centres who do not perform AC NAAT, additional samples must be shipped to STBRU using materials provided by STBRU. Details instructions are provided in the Trial Manual.

For all centres, any positive cultures must be shipped to STBRU using materials provided by STBRU. Detailed instructions are provided in the Trial Manual.

Blood samples taken for the immune response study and any blood samples taken for the optional pharmacokinetic study will be sent to the University of Birmingham for preparation, storage and analyses. Detailed instructions are provided in the Trial Manual.

The results of testing by the STBRU will be transferred directly to the NCTU. Participating centres will not be provided with copies of these results.

Full details of the laboratory assessments will be provided in the trial laboratory manual. This will include details of sample preparation, storage and transfer requirements.

11 Assessment of Efficacy

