17 HEALTH ECONOMICS

The economic analysis will compare the costs associated with the current standard treatment, ceftriaxone, with those of the proposed alternative treatment, gentamicin, in the treatment of gonorrhoea. Given that the primary objective of the trial is to determine non-inferiority of gentamicin, the economic analysis will focus on establishing whether the use of gentamicin rather than ceftriaxone is cost-neutral in the treatment of gonorrhoea. This will involve the examination of costs and resource use to determine whether there are any differences between the two treatments.

The economic evaluation will adopt the perspective of the health service (NHS), and data on resource use and costs will be collected prospectively within the study. Resource use data will be collected via a nurse / assessor completed form and will include questions on drug use, GP or other clinic visits etc. For a small random subset of patients in both arms of the trial we will collect information on the length of consultation required for delivery of the treatment therapy. This will be for the purpose of validation only, to confirm that the delivery of the treatment and length of consultation is not relevant to the drug being administered. Unit cost estimates will be applied to resource use data to generate individual level cost estimates. The sources of unit costs will include routine or published literature (e.g. PSSRU Unit costs of Health and Social Care).

The results will be reported in terms of the cost per patient successfully treated (measured in terms of microbial clearance of *Neisseria gonorrhoeae*). We will carry out a range of sensitivity analyses to explore the robustness of these results to plausible variations in key assumptions, and to consider the broader issue of the generalisability of the results.

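### Further gonorrhoea treatment between the injection and the visit 2 swab has no scoring rule: a re-treated participant who tests negative counts as cleared, and no planned analysis would show it

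*Protocol*

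**What the plan says.** Protocol section 14.2 makes intention-to-treat, without imputation, the primary approach. The only sensitivity analyses it plans concern missing primary outcomes. On adherence it argues that a single dose given straight after randomisation leaves almost no room for non-adherence, and concludes: "Therefore additional sensitivity analyses that aim to estimate treatment effect among those who have adhered with allocation are not expected to be required". The decision rule is: "Gentamicin will be regarded as non-inferior if the lower 95% confidence limit for the risk difference in confirmed clearance is -5 percentage points or greater".

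Sections 4.4 and 11 define clearance as a negative AC NAAT at every infected site two weeks after treatment. Neither mentions other antibiotics taken in between. Section 9.4 sets two weeks as the earliest time for visit 2 and gives no latest time. Section 8.8 restricts gentamicin and ceftriaxone only before randomisation. Sections 4.1 and 8.9 place further treatment of persisting infection outside the study, without saying how it affects the outcome.

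Three other places bear on the point:

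- Section 10.2: "The clinical management of the participant will be based on the results of local laboratory testing".
- Section 6.3, on withdrawal from study treatment: "If the participant did withdraw they would be treated according to their local clinical protocol". Such participants are still asked to attend at two weeks.
- Section 17, on the resource-use form: "will include questions on drug use, GP or other clinic visits etc".

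**The concern.** The argument for omitting an adherers' analysis answers one question, whether the allocated injection was given. It leaves open whether anything else was given before the outcome was measured. A participant whose infection persists, who attends somewhere unscheduled because of symptoms, is re-treated and then has a negative swab at visit 2 meets the definition of clearance as written. The success is credited to the randomised drug.

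In a superiority trial this would usually be conservative. Here it works the other way. If gentamicin fails more often, masking a given share of failures removes more of them from the gentamicin arm, and the difference moves toward zero. Expected failure rates are low, so a handful of re-scored participants can matter. The trial has one confirmatory conclusion, and no planned analysis would reveal the effect.

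**Working it through.** **Inputs from the protocol.** Clearance on ceftriaxone is 96% (section 14.1: "Based on an efficacy rate of 96% for the ceftriaxone regimen which is consistent with previous trials"). Size and power: "a total sample size of 646 for analysis (323 in each group) will achieve 90% power to detect non-inferiority". Alpha: "The significance level is 0.025", read as one-sided because it matches the lower limit of a two-sided 95% interval. The margin is -5 percentage points (section 14.2).

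**Input not in the protocol.** q is the share of true failures who are re-treated and test negative at visit 2. It is assumed, taken as equal in both arms, and varied.

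**Step 1: reproduce the sample size.** With equal true rates and unpooled variance,

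n per arm = (1.960 + 1.282)² × 2 × 0.96 × 0.04 / 0.05² = 322.8, rounded up to 323, or 646 in total.

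Power at 323 per arm is 90.0% by the normal approximation. For 10% loss, 646 / 0.9 = 717.8, so 718; the protocol rounds to 720. The stated figures are correct.

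**Step 2: effect on the difference.** Put the truth exactly at the margin, with failure rates of 4% and 9%. Observed clearance is 1 - 0.04(1 - q) on ceftriaxone and 1 - 0.09(1 - q) on gentamicin. The observed difference is -0.05(1 - q), so the true deficit shrinks by the factor (1 - q).

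**Step 3: chance of a false non-inferiority claim, 323 per arm.** The approximate column is Φ((d + 0.05)/SE - 1.960), where d is the observed difference. The exact column sums the two binomial distributions over all outcomes whose lower 95% Wald limit is at or above -5 points.

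| q | Difference (points) | Participants masked (ceftriaxone / gentamicin) | Approximate | Exact |
|---|---|---|---|---|
| 0% | -5.0 | 0 / 0 | 2.5% | 2.9% |
| 2% | -4.9 | 0.3 / 0.6 | 2.8% | 3.3% |
| 5% | -4.75 | 0.6 / 1.5 | 3.4% | 4.0% |
| 10% | -4.5 | 1.3 / 2.9 | 4.6% | 5.4% |
| 20% | -4.0 | 2.6 / 5.8 | 8.3% | 9.7% |
| 30% | -3.5 | 3.9 / 8.7 | 14.9% | 16.8% |

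Masked counts are 323 × 0.04 × q and 323 × 0.09 × q. For example, at q = 10% observed clearance is 96.4% and 91.9%, SE = √[(0.964 × 0.036 + 0.919 × 0.081)/323] = 0.0184, and Φ(0.005/0.0184 - 1.960) = 4.6%. The 2.9% at q = 0 is a property of the Wald interval at these rates and has nothing to do with re-treatment.

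**Step 4: which remedy removes the effect.** Scoring re-treated participants as not cleared restores the true difference of -5.0 points and the q = 0 row, with n unchanged. Excluding them, as a conventional per-protocol set would, still drops failures. Clearance becomes 0.96/(1 - 0.04q) and 0.91/(1 - 0.09q). At q = 20% the difference is -4.1 points and the approximate false-claim rate is 7.3%, against 8.3% with no remedy. At q = 10% it is 4.3% against 4.6%, and at q = 30% it is 12.6% against 14.9%. Exclusion alone leaves most of the bias.

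**The case against.** **The obvious rescue route is not in the protocol.** From sections 10.2 and 6.3 a reader might infer that local results lead to re-treatment before visit 2, or that withdrawals from treatment hide failures. Neither inference holds. Section 10.2 does not say when local results act. Tables 1 and 2 schedule post-treatment swabs only at visit 2, when the outcome swab is also taken; treatment prompted by those results comes too late to change it. Local results that arrive earlier are baseline results and cannot show failure. Section 6.3 concerns refusal of a single dose, which it calls unlikely, and that is the non-receipt section 14.2 already addresses. What remains is unscheduled attendance for persisting symptoms. The protocol does not describe it, although the resource-use form asks about other visits, and asymptomatic participants would have no symptoms to prompt it. This part of the objection stands and narrows the point.

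**The size depends wholly on q.** Nothing in the protocol supports 10% to 30%. A participant re-treated shortly before visit 2 might also still test positive. This stands.

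**The statistical analysis plan may settle it.** Sections 14 and 16.4 promise a full plan approved before unblinding, and the wording in 14.2 does not forbid an adherers' analysis. This stands in part. The protocol is not merely silent: it gives a reason that does not reach the case, alongside an endpoint definition that, read literally, scores the case as success.

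**A second success criterion would cost power.** If a per-protocol set lost 10% or 20% of the 323 per arm (assumed), exact power on that set would fall from 89.8% to about 86% or 82%. This stands, and the fix avoids it.

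**Conclusion.** The point holds in limited form. The reason given in section 14.2 does not cover treatment after the injection, and the endpoint definition counts a re-treated, then negative, participant as cleared. If gentamicin is truly worse and masking is similar in the two arms, the bias is toward non-inferiority. With true rates of 96% v 91%, the direction would reverse only if the masked share on ceftriaxone exceeded 0.09/0.04 = 2.25 times that on gentamicin.

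The false-claim rate rises from 2.9% to 4.0% at q = 5%, 5.4% at 10% and 9.7% at 20%. All of these rest on an assumed q, equal in both arms, with the truth at the margin. A reader might conclude that the trial's result will be materially biased or that the plan cannot stand unchanged. The documents do not support that: they give no re-treatment frequency, the interval is planned at about two weeks, and q may be close to zero. The sample size is correct and unaffected. This is a recommended improvement.

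**What to change.** Change analysis wording only.

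1. In sections 11 and 14.2, state that a participant given further treatment for persisting gonorrhoea before the visit 2 swab is scored as not cleared, whatever the swab shows. Confirm that the visit 2 form records the agent, reason and date. Section 17 shows that drug use and other visits are asked about for costing, but not that these details are captured.

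2. Replace the sentence waiving the adherers' analysis with a planned supportive per-protocol analysis: allocated drug received, infection AC-confirmed at baseline, and participants re-treated for persisting gonorrhoea kept in as failures. Report it beside intention-to-treat and check that the two agree. Do not make it a second formal success criterion.

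The cost is one extra analysis, a slightly stricter endpoint and possibly a few added fields on the visit 2 form. The recruitment target and the decision rule stay as they are. Both changes should be fixed before unblinding.

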1 BACKGROUND INFORMATION

N. gonorrhoeae readily develops resistance to antibiotic regimens. There are now high levels of resistance against penicillins, sulphonamides, tetracyclines and quinolones, all of which are no longer recommended for use. Current guidance from the British Association for Sexual Health and HIV is to treat with ceftriaxone (given with adjunctive azithromycin). Recent surveillance data show a reduction in sensitivity to ceftriaxone with an upward drift in the minimum inhibitory concentration [MIC] (13% with MIC over 0.03mg/l in 2010 cf. 1% in 2007) i.e. the proportion of cases which remain highly sensitive to ceftriaxone is decreasing over time[1]. Sporadic clinical failure of cephalosporins has been reported from Japan, Sweden, Spain and France [2] [3] [4] [5] [6]. The same reduction in antibiotic sensitivity was followed by widespread clinical failure within a few years for other antimicrobials (penicillin, tetracyclines and quinolones) used to treat gonorrhoea. Options to treat gonorrhoea are severely limited if cephalosporins become ineffective. With the exception of gentamicin, alternative agents have not been assessed in vivo (e.g. ertapenem, solithromycin)[7] [8] [9] [10], are reserved for specific infections (e.g. rifampicin for tuberculosis) [11] or have the potential to rapidly develop resistance (e.g. spectinomycin) [12].

The efficacy of gentamicin to treat gonorrhoea has been reported in small observational or controlled trials which date from the 1970s/80s, and all have a significant risk of bias [13] [14] [15] [16] [17] [18] [19] [20] [21] [22] Clinical and microbiological cure rates range from 65-100%. No adverse events were reported in these studies. No data are available on the efficacy of gentamicin when treating gonorrhoea in the pharynx or rectum, although antibiotics are sometimes less effective at these sites. A recent systematic review on gentamicin monotherapy found 3 studies (including 1 randomised controlled trial (RCT)) with cure rates of 91-95%, but the studies were small and had a significant risk of bias[23].

Gentamicin is usually bacteriocidal in action. Although the exact mechanism of action has not been fully elucidated, the drug appears to inhibit protein synthesis in susceptible bacteria by irreversibly binding to 30S ribosomal subunits. In general, gentamicin is active against many aerobic gram-negative bacteria and some aerobic gram-positive bacteria.

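### Section 14.2 asks whether treatment efficacy differs by infection site but fixes an output with no between-arm difference at any site

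*Protocol*

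**What the plan says.** Section 14.2 states the aim: "We are interested in whether treatment efficacy differs by site of infection". It notes that participants may be infected at more than one site, which gives as many as seven patterns, and then fixes the method: "we will separately estimate clearance by treatment arm along with 95% confidence intervals, rather than formally fit an interaction term". The rest of that sentence limits the declined interaction to the combinations of infection site. The section adds that any apparent differential effect would need confirmation in later research.

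The same section names a between-arm estimate, the risk difference with its 95% confidence interval, for the overall primary outcome only. Non-inferiority is declared if "the lower 95% confidence limit for the risk difference in confirmed clearance is -5 percentage points or greater". Sections 4.4 and 11 define that outcome as NAAT-negative at every infected site, so all sites enter one result.

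Section 1 explains why site matters: "No data are available on the efficacy of gentamicin when treating gonorrhoea in the pharynx or rectum". It adds that antibiotics sometimes work less well there.

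**The concern.** Whether efficacy differs by site is a question about how the gentamicin minus ceftriaxone difference varies between genital, pharyngeal and rectal infection. The fixed output is six single-arm proportions with their intervals. It contains no difference.

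The protocol does not say how the two arms are to be compared at a site. The natural habit is to see whether the intervals overlap, and that is a weaker reading than an interval for the difference: two 95% intervals can overlap while the interval for their difference excludes zero.

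The stated reason does not cover the gap. Seven infection patterns are a good reason not to fit a treatment-by-pattern interaction. They are no reason to omit a risk difference at each of three sites, which uses the counts already being tabulated.

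At stake is the reading of the result at the two sites for which the protocol says gentamicin has no earlier data. A positive overall result could be taken to cover them, with nothing beside it showing how far the arms differ there or how imprecisely that is known.

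**Working it through.** **1. The protocol's own figure.** Section 14.1 gives: "Based on an efficacy rate of 96% for the ceftriaxone regimen"; "will achieve 90% power to detect non-inferiority"; "The significance level is 0.025"; margin 5 points. Taking gentamicin also at 96% (not stated, but implied by the result):

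n per arm = (1.960 + 1.282)² × 2 × 0.96 × 0.04 / 0.05² = 10.507 × 0.0768 / 0.0025 = 322.8, so 323 per arm and 646 in total, as stated. Allowing for 10% loss, 646 / 0.9 = 718, against a stated 720. No stated figure is wrong. No figure is given for the analysis by infection site.

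**2. Overlap against difference.** The protocol gives neither the number infected at each site nor an expected gentamicin rate by site, so the counts below are assumptions. Single-arm intervals are Wilson. The interval for the difference is Newcombe, with limits

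d − √[(p_G − l_G)² + (u_C − p_C)²] and d + √[(u_G − p_G)² + (p_C − l_C)²].

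For 85/100 on gentamicin and 96/100 on ceftriaxone, in percentage points:
- Wilson: gentamicin 76.7 to 90.7, ceftriaxone 90.2 to 98.4. They overlap.
- d = 85 − 96 = −11.0.
- Lower limit: −11.0 − √(8.3² + 2.4²) = −19.6.
- Upper limit: −11.0 + √(5.7² + 5.8²) = −2.8 (from unrounded values).

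The same thing happens at other sizes:

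| Gentamicin | Ceftriaxone | Wilson, gentamicin | Wilson, ceftriaxone | Difference (95% CI) |
|---|---|---|---|---|
| 52/65 | 62/65 | 68.7 to 87.9 | 87.3 to 98.4 | −15.4 (−27.1 to −4.1) |
| 99/113 | 108/113 | 80.3 to 92.5 | 90.1 to 98.1 | −8.0 (−15.7 to −0.6) |

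**3. How often it matters.** Assume true clearance at a site of 96% on ceftriaxone and 85% on gentamicin, with 20, 35 or 50% of 323 infected there (65, 113 or 162 per arm). Exact binomial probabilities, summed over all pairs of counts:

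| Per arm | Wilson intervals separate | Newcombe CI for the difference lies below zero |
|---|---|---|
| 65 | 25% | 57% |
| 113 | 54% | 82% |
| 162 | 75% | 94% |

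**4. What a site difference cannot do.** With 96% clearance in both arms, the half-width of the 95% CI at a site is 1.96 × √(2 × 0.96 × 0.04 / n). This is 6.7, 5.1 and 4.3 points for n = 65, 113 and 162. The chance of meeting a 5-point margin within the site is Φ(0.05 / √(2 × 0.96 × 0.04 / n) − 1.96), which gives 31%, 48% and 63%. Site differences are useful as estimates but are not precise enough for a site-level non-inferiority decision.

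**The case against.** The strongest reply is that this is an exploratory table, openly labelled as needing confirmation, and that whether it carries a difference column is the sort of detail a statistical analysis plan settles. Part of this stands. An analysis plan may add the difference, and the protocol does not forbid it. But the protocol is not silent here: it poses a comparative question and then specifies an output that is not comparative. A plan that follows it to the letter inherits the gap.

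It is also fair that the protocol states no overlap rule, and that the size of the illustration depends on the interval method. At 96/100 against 85/100 the Wilson intervals overlap by only about half a point, and Wald intervals would just separate (92.2% against 92.0%). The example shows what a reader may do with the planned output. It does not show something the protocol prescribes.

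A reader might go further in three ways that the documents do not support:
- **That the plan cannot answer the question.** Two proportions with their denominators allow a crude difference to be worked out. The output leaves that step to the reader.
- **That the plan hides pharyngeal failure.** Pharyngeal clearance is to be reported for each arm, so a low gentamicin rate would be in print. A pharyngeal failure also counts as a failure in the all-sites primary outcome.
- **That omitting the interaction is an error.** It is a deliberate choice with a reason given, and that reason is sound for an interaction over combinations.

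One can also calculate how often overall non-inferiority would be declared despite a deficit confined to the pharynx. With an assumed 11-point deficit the probability is 0.52, 0.38 and 0.26 at pharyngeal shares of 15, 20 and 25%. Those figures describe the pooled primary analysis. Adding site differences would not change them, so they do not measure this point.

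**Conclusion.** The point holds as a mismatch between question and output. Section 14.2 asks about a treatment effect by infection site and fixes per-arm clearance only, and its stated reason does not exclude a difference at each of three sites.

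The effect is on interpretation. Under the assumed rates of 96% and 85%, a reader relying on separation of the two arm intervals would see a difference in 25 to 75% of trials, against 57 to 94% for an interval on the difference, across 65 to 162 infected participants per arm. These figures rest on assumed site shares, assumed site rates and a choice of interval method, none of which the protocol gives.

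The primary analysis, its margin and the sample size are untouched. This is a modest improvement to an exploratory analysis, worth making because the protocol itself identifies the pharynx and rectum as sites without gentamicin data.

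**What to change.** In section 14.2, or in the statistical analysis plan:
- For genital, pharyngeal and rectal infection, report the gentamicin minus ceftriaxone risk difference with its 95% CI beside the per-arm clearance, and name the interval method.
- Label these estimates exploratory and attach no site-level non-inferiority decision rule. At these sizes such a rule would often fail an equally effective drug.
- State that the overall non-inferiority result does not by itself establish non-inferiority at each infection site.
- Optionally, add one treatment-by-site contrast over three sites, clustered on participant because one person can contribute to several sites. The protocol's reason for avoiding the seven-pattern interaction can stand.

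The cost is a few lines of text and a little analysis, with no new data and no change to the sample size. The site intervals will be wide and should be presented as such.
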